1.1. Trial Design

This is an open-label, multicenter, Phase 2 study in subjects at least 18 years of age with MCL, DLBCL, or FL. Approximately 210 subjects may be enrolled, with up to 100 subjects planned for MCL and up to 55 subjects each for DLBCL and FL.

This study will be conducted and analyzed separately for each subtype of NHL. A biomarker adaptive threshold design is implemented that enables testing of the overall population and the establishment of a biomarker-defined enriched population simultaneously. Two stages are planned.

Stage 1 of the study is designed to provide a preliminary assessment of activity at an early stage. Since CD38 expression level may be associated with daratumumab activity, Stage 1 will enroll subjects who have tumors where at least 50% of the cells are CD38 positive. This requirement seeks to mitigate the possibility that a low response rate observed in Stage 1 might be due to low levels of CD38 expression. The selection of the 50% cut-off is based on the existing CD38 expression level data in these NHL subtypes as well as practical considerations. At the end of Stage 1, which is expected to be 6 months after the last subject is enrolled in each NHL subtype, or earlier if emerging data allows, an interim analysis will be conducted. The purpose of the interim analysis is to evaluate efficacy and safety data in Stage 1. The efficacy assessment will be focused on ORR. In case of low ORR taking into consideration of CD38 expression level, an individual NHL subtype may be terminated for futility. The detailed futility stopping guideline is as follows.

- For MCL, if at least 5 out of 20 subjects have achieved CR or PR after Stage 1, then Stage 2 may be initiated. For DLBCL, if at least 4 out of 15 subjects have achieved CR or PR after Stage 1, then Stage 2 may be initiated. For FL, if at least 7 out of 15 subjects have achieved CR or PR after Stage 1, then Stage 2 may be initiated.
- For MCL, if at most 4 out of 20 subjects have achieved CR or PR after Stage 1, consider terminating MCL for futility. For DLBCL, if at most 3 out of 15 subjects have achieved CR or PR after Stage 1, consider terminating DLBCL for futility. For FL, if at most 6 out of 15 subjects have achieved CR or PR after Stage 1, consider terminating FL for futility.

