Alternatively, if the futility criteria are not met and if supported by the totality of the Stage 1 data, Stage 2 for that NHL subtype may be opened for accrual. If the required number of responses is observed prior to completion of enrollment in Stage 1, Stage 2 may be opened immediately upon completion of enrollment to Stage 1, if supported by the totality of data.

Stage 2, if opened, is designed to further evaluate safety and efficacy as well as to determine a threshold for CD38 expression that is associated with enhanced daratumumab activity. Supported by the preliminary activity observed in Stage 1, Stage 2 will enroll any subject in each NHL subtype. To mitigate the possibility that a low response may be observed due to low levels of

CD38 expression in enrolled subjects, the number of Stage 2 subjects with CD38 expression level <50% will be capped within each NHL subtype.

The target number of subjects in each stage by CD38 expression level is shown in table below.

Type of NHL	Number of Subjects			Overall Total
	Stage 1 CD38 expression level ^b ≥50%	Stage 2 (optional)		
		CD38 expression level ^a <50%	CD38 expression level ^b ≥50%	
MCL	20	≤30	≥50	100
DLBCL	15	≤20	≥20	55
FL	15	≤20	≥20	55

DLBCL=diffuse large B cell lymphoma ; FL=follicular lymphoma; MCL= mantle cell lymphoma

a. These subjects have tumors where <50% of the cells are positive for CD38 by immunohistochemistry.

[figure not shown]
b. These subjects have tumors where ≥50% of the cells are positive for CD38 by immunohistochemistry.

Subject participation will include a Screening Phase, a Treatment Phase, and a Follow-up Phase.

The Screening Phase will be up to 28 days prior to Cycle 1, Day 1. Prior to enrollment, subjects are required to provide tumor tissue to determine CD38 expression level by immunohistochemistry (IHC) at a central laboratory. An additional fresh biopsy should be obtained whenever possible even if an archival sample is provided.

The Treatment Phase will extend from Cycle 1, Day 1 until study drug discontinuation. After first dose, disease evaluations will occur every 8 weeks for the first 3 evaluations, then every 16 weeks for the next two evaluations and then every 24 weeks thereafter. Subjects will be treated until disease progression, unacceptable toxicity, or other reasons as listed in the protocol.

A schematic overview of the dosing schedule is presented as follows.

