1.2. Sample Size Justification

Within each subtype of NHL, a biomarker adaptive threshold design (Jiang 2007)² is to be utilized, which allows identification of a biomarker threshold based on data analysis in parallel with the statistical testing of the ORR for proof-of-concept. That is, the proof-of-concept could be established either in the overall population or in the subpopulation of subjects as identified by the biomarker (CD38 expression level) threshold. In order to provide an early futility check within each NHL subtype, a two-stage procedure is also incorporated.

Given that there are two potential pathways for proof-of-concept and the inherent multiple testing issues associated with the selection of the biomarker threshold, per the recommendation by Jiang (2007)², the powering for MCL will be based on the overall population with an overall alpha of 0.04, which preserves the power of the overall test while providing a reasonable power against a strong subset effect at the same time with the remaining alpha of 0.01. Since further randomized Phase 2 proof-of-concept studies in combination with other agents are likely required for DLBCL and FL, an alpha of 0.05 is used for the overall population in these two subtypes.

In Stage 1, a total of 50 subjects will be enrolled for all 3 NHL types combined. In Stage 2, a maximum of 160 subjects may be enrolled if all three tumor types are expanded, bringing the maximal sample size to 210 with all tumor types combined.

For MCL, the null hypothesis is that the ORR is at most 20%, and the alternative hypothesis is that the ORR is at least 35% for all subjects, or at least 40% for those subjects whose CD38 expression level is above a to-be-determined level. These are based on the fact that some recent approvals in previously treated MCL were based on an ORR of approximately 31% for bortezomib and 26% for lenalidomide. Up to 100 MCL subjects with positive CD38 expression may be enrolled. Seventy (70) of those must have tumors with 50% or more cells positive for CD38 expression at baseline in order to rule out that any lack of activity is mostly due to low CD38 expression level in the enrolled subjects.

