For DLBCL, the null hypothesis is that the ORR is at most 15%, and the alternative hypothesis is that the ORR is at least 30% for all subjects, or at least 40% for those subjects whose CD38 expression level is above a to-be-determined level. These were based on the clinical observation that relapsed DLBCL subjects who are not eligible for HDT/ASCT have a very poor prognosis and no established therapeutic options.

For FL, the null hypothesis is that the ORR is at most 30%, and the alternative hypothesis is that the ORR is at least 50% for all subjects, or at least 60% for those subjects whose CD38 expression level is above a to-be-determined level. These are based on the published ORRs of idelalisib (54%, which was the basis of an accelerated approval in the U.S.) and rituximab monotherapy (49%, Coiffier 2011).

For both DLBCL and FL, 55 subjects may be enrolled. Thirty-five (35) of those must have tumors with 50% or more cells positive for CD38 expression at baseline in order to rule out that any lack of activity is mostly due to low CD38 expression level in the enrolled subjects.

The trial will be carried out in two stages within each NHL subtype, as in a Simon's two-stage design. Each NHL subtype, independent of the other subtypes, may be discontinued after Stage 1 due to futility. To exclude the possibility that an observed low response rate is due to low CD38 expression level at baseline, the trial will enroll sufficient number of subjects with tumors where $\geq 50\%$ of cells are CD38 positive in both stages. The detailed procedure will proceed as follows.

For MCL, Stage 1 will accrue 20 subjects with tumors where $\geq 50\%$ of cells are CD38 positive. If the futility criteria are met (at most 4 responses overall), no further expansion is planned. Otherwise, an additional 80 subjects will be enrolled to Stage 2; at least 50 of these subjects will have tumors where $\geq 50\%$ of cells are CD38 positive. The sample size will provide approximately 85% power to reject the null hypothesis for the overall population with a one-sided significance level of 0.04.

For DLBCL, Stage 1 will accrue 15 subjects with tumors where $\geq 50\%$ of cells are CD38 positive. If the futility criteria are met (at most 3 responses overall), no further expansion is planned. Otherwise, an additional 40 subjects will be enrolled to Stage 2; at least 20 of these

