subjects will have tumors where $\geq 50\%$ of cells are CD38 positive. The sample size will provide approximately 80% power to reject the null hypothesis for the overall population with a one-sided significance level of 0.05.

For FL, Stage 1 will accrue 15 subjects with tumors where $\geq 50\%$ of cells are CD38 positive. If the futility criteria are met (at most 6 responses overall), no further expansion is planned. Otherwise, an additional 40 subjects will be enrolled to Stage 2; at least 20 of these subjects will have tumors where $\geq 50\%$ of cells are CD38 positive. The sample size will provide approximately 80% power to reject the null hypothesis for the overall population with a one-sided significance level of 0.05.

At the end of the study, all available data for each particular NHL subtype will be analyzed to determine a CD38 expression threshold for that subtype, which will be used to define an enriched population, via statistical inference.

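### The SAP leaves open whether the Stage 1 futility rule is binding, so alpha 0.05 for DLBCL and FL is conditional and the stated 80% power is not reached with the rule enforced at the overall response rates

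*SAP*

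**What the plan says.** SAP 1.1 (Trial Design) introduces the Stage 1 counts as a guideline. With at most 3 of 15 DLBCL responders the sponsor is to "consider terminating DLBCL for futility"; FL (at most 6 of 15) and MCL (at most 4 of 20) are worded alike. The same section then opens Stage 2 "if the futility criteria are not met and if supported by the totality of the Stage 1 data".

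SAP 1.2 (Sample Size Justification) likens the procedure to Simon's two-stage design. For DLBCL: "If the futility criteria are met (at most 3 responses overall), no further expansion is planned". For FL: "If the futility criteria are met (at most 6 responses overall), no further expansion is planned". Otherwise 40 more subjects are enrolled in each. Yet SAP 1.2 also says, permissively, that a subtype can be dropped after Stage 1. Neither section says binding or non-binding.

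On error rates, "an alpha of 0.05 is used for the overall population in these two subtypes", and 55 subjects per subtype are said to give "approximately 80% power to reject the null hypothesis for the overall population with a one-sided significance level of 0.05". MCL is given about 85% power at one-sided 0.04. The available text states no number of responses needed to reject the null in any subtype. The SAP Introduction limits the document to the interim futility analyses; it becomes the study SAP only if futility is met.

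**The concern.** A subtype stopped at Stage 1 cannot reject its null. A final limit derived with enforced stopping can therefore be lower than a single-stage limit and still hold alpha. That credit disappears if the sponsor continues after a missed boundary. Without knowing whether the rule binds, and without the final limit, a reader cannot confirm the stated alpha.

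The same ambiguity affects power. An enforced rule discards every trial that misses Stage 1, including those of an active drug, so a stated power has meaning only under a stated reading of the rule.

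**Working it through.** **Inputs (SAP 1.2; cut-offs also in SAP 1.1)**

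| | n1 | stop if ≤ r1 | n | p0 | p1 | alpha | stated power |
|---|---|---|---|---|---|---|---|
| MCL | 20 | 4 | 100 | 0.20 | 0.35 | 0.04 | 85% |
| DLBCL | 15 | 3 | 55 | 0.15 | 0.30 | 0.05 | 80% |
| FL | 15 | 6 | 55 | 0.30 | 0.50 | 0.05 | 80% |

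**Formulas.** Rule followed: P(reject) = sum over x from r1+1 to n1 of P(X1 = x) × P(X2 ≥ c − x), with X1 ~ Bin(n1, p), X2 ~ Bin(n − n1, p) and final limit c. Rule never enforced: P(X ≥ c), X ~ Bin(n, p). Size is taken at p0 and power at p1.

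**Step 1: the plan's power figures, rule followed.** I took the smallest c that holds alpha.
- MCL: c = 27 gives size 0.041 (too large); c = 28 gives 0.026 and power 84.7%. The stated 85% reproduces.
- DLBCL: c = 12 gives 0.056; c = 13 gives 0.034 and power 66.3%.
- FL: c = 20 gives 0.065; c = 21 gives 0.048 and power 69.0%.

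No choice of c rescues the last two, because power cannot exceed the chance of passing Stage 1:
- DLBCL: 1 − P(X1 ≤ 3 | 15, 0.30) = 1 − 0.297 = 0.703.
- FL: 1 − P(X1 ≤ 6 | 15, 0.50) = 1 − 0.304 = 0.696.

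Other readings tried: a single-stage exact test gives DLBCL 81.0% (c = 14), which matches, and FL 91.1% (c = 23), which does not. Enforced cut-offs one lower give DLBCL 80.0% (≤2/15, c = 13) and FL 82.4% (≤5/15, c = 22), but those are not the written cut-offs.

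**Step 2: size at limits that take credit for stopping.** These limits are assumed, as none is stated.

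| | c | followed | overridden only one response short | never enforced |
|---|---|---|---|---|
| MCL | 28/100 | 0.026 | 0.031 | 0.034 |
| DLBCL | 13/55 | 0.034 | 0.049 | 0.060 |
| FL | 21/55 | 0.048 | 0.076 | 0.121 |

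If a missed boundary were overridden with a fixed probability, whatever the count, size would reach 0.05 at about 61% for DLBCL and about 3% for FL.

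**Step 3: limits without credit for stopping.** The smallest c with P(X ≥ c | n, p0) ≤ alpha:

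| | c | size, never enforced | size, followed | power, followed | power, never enforced |
|---|---|---|---|---|---|
| MCL | 28/100 | 0.034 | 0.026 | 84.7% | 94.4% |
| DLBCL | 14/55 | 0.030 | 0.019 | 62.7% | 81.0% |
| FL | 23/55 | 0.042 | 0.021 | 67.0% | 91.1% |

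**Step 4: the Stage 1 response rate.** Step 3 uses one rate in both stages, but Stage 1 enrols only tumours with at least 50% CD38-positive cells. As an illustration, let Stage 1 respond at the enriched rate in SAP 1.2 (40% DLBCL, 60% FL) with the overall rate held. Stage 2 then responds at (55 × 0.30 − 15 × 0.40)/40 = 0.2625 for DLBCL and (55 × 0.50 − 15 × 0.60)/40 = 0.4625 for FL. With the rule followed at 14/55 and 23/55, power is about 77% and 85%.

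**The case against.** A reader might infer that SAP 1.1 is discretionary, SAP 1.2 is binding, and the plan's type I error is therefore 0.060 in DLBCL and 0.121 in FL. The documents do not support that, for four reasons.

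- **The split is not clean.** SAP 1.2 has permissive wording of its own, and SAP 1.1 ties Stage 2 to the criteria not being met. The added appeal there to the totality of the data only allows Stage 2 to be declined after a pass, which lowers type I error. No passage describes opening Stage 2 after a missed boundary.
- **The limits are assumed.** 13/55 and 21/55 appear nowhere in the text. At 14/55 and 23/55 alpha holds under either reading, and for DLBCL the single-stage 14/55 fits the stated 80% better than an enforced 13/55.
- **The largest figures are an extreme.** They require continuing at every Stage 1 count, even zero responders. An override one response short leaves DLBCL at 0.049.
- **Scope.** This SAP covers the interim. Protocol 11.2 and 11.9, on sample size and interim analysis, are not in the available text and may state limits.

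It would likewise be too strong to say that true power is 63% to 67%: those figures assume Stage 1 responds at the overall rate. The SAP also expects further randomized studies in DLBCL and FL, which lowers the stakes.

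All of this limits the claim. It does not remove the need to state the rule's status: this SAP governs the futility decision and itself states the alpha and power.

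**Conclusion.** The point stands as a conditional one. The SAP does not settle whether the rule binds, and alpha of 0.05 for DLBCL and FL holds only if the rule is always followed or the final limit takes no credit for stopping. Exceeding 0.05 needs both an override and a limit that relies on stopping. FL is the sensitive subtype, since at 21/55 even a one-response override exceeds 0.05. MCL is unaffected at 28/100.

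The power discrepancy depends on no assumed final limit. With the written cut-offs enforced at the stated overall response rates, about 80% cannot be reached in DLBCL or FL, while MCL's 85% reproduces on that same basis. It does rest on a homogeneous response rate across stages; an enriched Stage 1 largely closes the gap, but the SAP does not say that its power was computed that way. The three subtypes' figures do not all reproduce under one reading of the rule at a homogeneous rate.

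**What to change.** Use one wording in SAP 1.1 and 1.2, and settle it before Stage 1 results are reviewed.

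- **If discretion is kept:** declare the rule non-binding and set the final limits without credit for stopping: MCL ≥28/100, DLBCL ≥14/55, FL ≥23/55. Check them against any limits in protocol 11.2 and 11.9.
- **If the rule is to bind:** remove the permissive wording. The smallest valid limits are then 28/100, 13/55 and 21/55, with power 84.7%, 66.3% and 69.0% at a homogeneous response rate.
- **In either case:** restate power with its assumptions. For the non-binding option, give the range between the rule followed and never enforced (MCL 84.7% to 94.4%, DLBCL 62.7% to 81.0%, FL 67.0% to 91.1%, homogeneous rate), with the enriched Stage 1 case (about 77% for DLBCL and 85% for FL, rule followed) shown separately.

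No extra subjects or data are needed. The cost is an SAP revision that commits to final limits, and a less favourable stated power for DLBCL and FL.

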1.2. Sample Size Justification

Within each subtype of NHL, a biomarker adaptive threshold design (Jiang 2007)² is to be utilized, which allows identification of a biomarker threshold based on data analysis in parallel with the statistical testing of the ORR for proof-of-concept. That is, the proof-of-concept could be established either in the overall population or in the subpopulation of subjects as identified by the biomarker (CD38 expression level) threshold. In order to provide an early futility check within each NHL subtype, a two-stage procedure is also incorporated.

Given that there are two potential pathways for proof-of-concept and the inherent multiple testing issues associated with the selection of the biomarker threshold, per the recommendation by Jiang (2007)², the powering for MCL will be based on the overall population with an overall alpha of 0.04, which preserves the power of the overall test while providing a reasonable power against a strong subset effect at the same time with the remaining alpha of 0.01. Since further randomized Phase 2 proof-of-concept studies in combination with other agents are likely required for DLBCL and FL, an alpha of 0.05 is used for the overall population in these two subtypes.

In Stage 1, a total of 50 subjects will be enrolled for all 3 NHL types combined. In Stage 2, a maximum of 160 subjects may be enrolled if all three tumor types are expanded, bringing the maximal sample size to 210 with all tumor types combined.

For MCL, the null hypothesis is that the ORR is at most 20%, and the alternative hypothesis is that the ORR is at least 35% for all subjects, or at least 40% for those subjects whose CD38 expression level is above a to-be-determined level. These are based on the fact that some recent approvals in previously treated MCL were based on an ORR of approximately 31% for bortezomib and 26% for lenalidomide. Up to 100 MCL subjects with positive CD38 expression may be enrolled. Seventy (70) of those must have tumors with 50% or more cells positive for CD38 expression at baseline in order to rule out that any lack of activity is mostly due to low CD38 expression level in the enrolled subjects.

For DLBCL, the null hypothesis is that the ORR is at most 15%, and the alternative hypothesis is that the ORR is at least 30% for all subjects, or at least 40% for those subjects whose CD38 expression level is above a to-be-determined level. These were based on the clinical observation that relapsed DLBCL subjects who are not eligible for HDT/ASCT have a very poor prognosis and no established therapeutic options.

For FL, the null hypothesis is that the ORR is at most 30%, and the alternative hypothesis is that the ORR is at least 50% for all subjects, or at least 60% for those subjects whose CD38 expression level is above a to-be-determined level. These are based on the published ORRs of idelalisib (54%, which was the basis of an accelerated approval in the U.S.) and rituximab monotherapy (49%, Coiffier 2011).

For both DLBCL and FL, 55 subjects may be enrolled. Thirty-five (35) of those must have tumors with 50% or more cells positive for CD38 expression at baseline in order to rule out that any lack of activity is mostly due to low CD38 expression level in the enrolled subjects.

The trial will be carried out in two stages within each NHL subtype, as in a Simon's two-stage design. Each NHL subtype, independent of the other subtypes, may be discontinued after Stage 1 due to futility. To exclude the possibility that an observed low response rate is due to low CD38 expression level at baseline, the trial will enroll sufficient number of subjects with tumors where $\geq 50\%$ of cells are CD38 positive in both stages. The detailed procedure will proceed as follows.

For MCL, Stage 1 will accrue 20 subjects with tumors where $\geq 50\%$ of cells are CD38 positive. If the futility criteria are met (at most 4 responses overall), no further expansion is planned. Otherwise, an additional 80 subjects will be enrolled to Stage 2; at least 50 of these subjects will have tumors where $\geq 50\%$ of cells are CD38 positive. The sample size will provide approximately 85% power to reject the null hypothesis for the overall population with a one-sided significance level of 0.04.

For DLBCL, Stage 1 will accrue 15 subjects with tumors where $\geq 50\%$ of cells are CD38 positive. If the futility criteria are met (at most 3 responses overall), no further expansion is planned. Otherwise, an additional 40 subjects will be enrolled to Stage 2; at least 20 of these

subjects will have tumors where $\geq 50\%$ of cells are CD38 positive. The sample size will provide approximately 80% power to reject the null hypothesis for the overall population with a one-sided significance level of 0.05.

For FL, Stage 1 will accrue 15 subjects with tumors where $\geq 50\%$ of cells are CD38 positive. If the futility criteria are met (at most 6 responses overall), no further expansion is planned. Otherwise, an additional 40 subjects will be enrolled to Stage 2; at least 20 of these subjects will have tumors where $\geq 50\%$ of cells are CD38 positive. The sample size will provide approximately 80% power to reject the null hypothesis for the overall population with a one-sided significance level of 0.05.

At the end of the study, all available data for each particular NHL subtype will be analyzed to determine a CD38 expression threshold for that subtype, which will be used to define an enriched population, via statistical inference.

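### The stated 80% power for DLBCL and FL does not agree with the written futility boundaries, which cap power at 70.3% and 69.6% under the stated overall ORRs

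*SAP*

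**What the plan says.** SAP section 1.2 sets up each subtype as a two-stage trial: "The trial will be carried out in two stages within each NHL subtype, as in a Simon's two-stage design".

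- **DLBCL.** The null ORR is at most 15%; "the alternative hypothesis is that the ORR is at least 30% for all subjects". Stage 1 has 15 subjects. "If the futility criteria are met (at most 3 responses overall), no further expansion is planned"; otherwise 40 more are enrolled.
- **FL.** The null ORR is at most 30%; "the alternative hypothesis is that the ORR is at least 50% for all subjects". Stage 1 has 15 subjects. "If the futility criteria are met (at most 6 responses overall), no further expansion is planned"; otherwise 40 more are enrolled.
- **Power, both cohorts.** "The sample size will provide approximately 80% power to reject the null hypothesis for the overall population", at one-sided 0.05.
- **MCL, for comparison.** The null is 20% and the overall alternative 35%, with 20 + 80 subjects and a stop at 4 or fewer responses. "The sample size will provide approximately 85% power to reject the null hypothesis for the overall population with a one-sided significance level of 0.04".

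SAP section 1.1 gives the same boundaries in softer terms, for example "For DLBCL, if at most 3 out of 15 subjects have achieved CR or PR after Stage 1, consider terminating DLBCL for futility". It also restricts Stage 1 to tumours with at least 50% CD38-positive cells. The text available for this review gives no final rejection cut-off and no separate Stage 1 response rate for the power calculation. Protocol section 11.2 (sample size) was not part of that text.

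**The concern.** A cohort stopped at Stage 1 cannot reject its null hypothesis, so power cannot be greater than the probability of passing Stage 1. At the stated overall alternatives, the DLBCL boundary (20% observed, against a true 30%) and the FL boundary (40% observed, against a true 50%) each sit only 10 percentage points below the true rate, with 15 subjects. Stopping by chance is then common, and 80% power looks out of reach.

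An 80% figure tells the reader that a drug with the target ORR is missed about one time in five. If the true figure is nearer one in three, and nearly all of the loss arises at Stage 1, the go/no-go rule is stricter than the plan says. This SAP is written for those futility analyses, and it becomes the study SAP if futility is met.

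**Working it through.** **Inputs** (all from SAP 1.2; r1 is the largest Stage 1 count that stops the cohort)

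| | p0 | p1 | n1 | r1 | n | one-sided alpha | stated power |
|---|---|---|---|---|---|---|---|
| MCL | 0.20 | 0.35 | 20 | 4 | 100 | 0.04 | 85% |
| DLBCL | 0.15 | 0.30 | 15 | 3 | 55 | 0.05 | 80% |
| FL | 0.30 | 0.50 | 15 | 6 | 55 | 0.05 | 80% |

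**Formulas** (exact binomial)

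- Stopping probability: P(X1 ≤ r1 | n1, p1). The ceiling on power is 1 minus this.
- Power: sum over x1 > r1 of P(X1 = x1) × P(X2 ≥ c − x1), at p1. The cut-off c is the smallest total for which the same sum at p0 is within alpha. The cut-offs are derived here.

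**Step 1. Check the method on MCL.** P(X1 ≤ 4 | 20, 0.35) = 0.118. The cut-off is 28/100 (type I error 0.026), and power is 84.7%. This reproduces the stated 85%, with the futility rule applied and the overall ORR used in both stages. Ignoring futility would give 94.4%.

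**Step 2. Ceilings for DLBCL and FL.**

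- DLBCL: P(X1 ≤ 3 | 15, 0.30) = 0.2969, so the ceiling is 1 − 0.2969 = 70.3%.
- FL: P(X1 ≤ 6 | 15, 0.50) = (1 + 15 + 105 + 455 + 1365 + 3003 + 5005) / 32768 = 9949 / 32768 = 0.3036, so the ceiling is 69.6%.

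**Step 3. Full two-stage power.**

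- DLBCL: cut-off 13/55 (type I error 0.034), power 66.3%. The miss rate is 33.7%: 29.7% from stopping and 4.0% from the final test.
- FL: cut-off 21/55 (type I error 0.048), power 69.0%. The miss rate is 31.0%: 30.4% from stopping and 0.6% from the final test.

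**Step 4. Other readings that might give 80 / 80 / 85.**

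| Reading | DLBCL | FL | MCL |
|---|---|---|---|
| Stated in SAP | 80% | 80% | 85% |
| Boundaries as written, overall ORR in both stages | 66.3% | 69.0% | 84.7% |
| Futility ignored (single-stage exact test) | 81.0% | 91.1% | 94.4% |
| Stage 1 at an assumed CD38-high rate of 40% / 60% / 40%, overall ORR held fixed | 83.9% | 89.2% | about 91% |
| DLBCL and FL boundaries one response lower (≤2/15, ≤5/15), MCL as written | 80.0% | 82.4% | 84.7% |

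For DLBCL and FL the fourth row takes Stage 2 as 20 high and 20 low expressors, so that 35 of 55 are high. Holding the overall ORR fixed then makes the low-expressor rate (55 × 0.30 − 35 × 0.40) / 20 = 12.5% in DLBCL and (55 × 0.50 − 35 × 0.60) / 20 = 32.5% in FL. Stage 1 stopping falls to 9.1% and 9.5%.

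In the last row, stopping is 12.7% (DLBCL) and 15.1% (FL), with type I error 0.049 and 0.0499. The next cut-off up for FL, 23/55, gives 80.2%.

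**Step 5. Stage 1 rate needed for 80%.** Solving P(X1 ≤ 3 | 15, q) = 0.20 gives q = 33.7% for DLBCL. Solving P(X1 ≤ 6 | 15, q) = 0.20 gives q = 54.2% for FL. Below these rates the ceiling alone rules out 80%, whatever happens in Stage 2.

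**The case against.** The strongest objection is enrichment. Stage 1 enrols only CD38 ≥50% tumours because expression may be linked to activity, while the 30% and 50% alternatives describe all subjects. If high expressors respond better, the boundaries and 80% power can both hold. With the overall ORR fixed and 20 high plus 20 low expressors in Stage 2, power reaches 80% at a high-expressor rate of about 37% in DLBCL and 54.6% in FL. Both are below the 40% and 60% that SAP 1.2 quotes for subjects above the CD38 threshold. This stands as a possibility, and the ceilings are conditional on it. It does not explain the stated figures. SAP 1.2 gives no Stage 1 rate as a power input, its 40% and 60% belong to a threshold still to be determined, and the same assumption lifts MCL to about 91% against 85% stated.

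The second objection is that section 1.1 words stopping as guidance. With futility treated as non-binding, DLBCL power is 81.0%, which matches the SAP. FL at 91.1% and MCL at 94.4% do not match, and section 1.2 uses firmer wording. FL is therefore the clearer of the two discrepancies.

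Third, Protocol 11.2 may give cut-offs or assumptions not seen here. A final cut-off cannot lift a Stage 1 ceiling; a stated Stage 1 rate could.

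Finally, the match with boundaries one response lower is an inference. The written boundaries are consistent across sections 1.1 and 1.2, and nothing in the documents says that they are wrong.

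**Conclusion.** The concern holds. With the written boundaries followed and the overall alternative ORR in both stages, power is 66.3% for DLBCL and 69.0% for FL against the stated 80%: shortfalls of about 14 and 11 points, too large for the word approximately to cover. The arithmetic is exact. The result rests on two conditions, that the futility guideline is applied and that Stage 1 subjects respond at the overall rate. Those same conditions reproduce the SAP's own MCL figure. No single alternative tested that keeps the written boundaries matches all three cohorts. The pattern suggests that the DLBCL and FL power figures and boundaries come from different calculations, but the documents do not show which is in error.

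**What to change.** Show the power calculation for DLBCL and FL in SAP 1.2, including the final cut-offs, and make it agree with the boundaries in sections 1.1 and 1.2.

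- If the boundaries stand, either restate power as about 66% (DLBCL) and 69% (FL) under a uniform overall ORR, or state the Stage 1 response rate assumed for CD38 ≥50% subjects and the power it gives.
- If the 80% was calculated with other boundaries, say so and reconcile the passages.
- In either case, say whether the stated power assumes that the futility guideline is followed, and align the wording of sections 1.1 and 1.2 on that point.

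Sample size does not change. If the boundaries stand, the cost is wording and a less favourable power figure. If the boundaries are what is in error, the correction alters a go/no-go rule and has to be settled before the Stage 1 data are reviewed.
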